8.1.3 Control arm (Comparator)

Control arm SMEs will not receive the intervention. However, in order to provide some form of compensation and incentive to take part in the study, control arm SMEs will receive the same summary data reports following data collection, and champion training post-study evaluations, that are also provided to the intervention group SMEs. These reports offer insights into the workforce's health and wellbeing, along with recommendations for independent, future action on employee health and wellbeing. To limit the risk that employee outcome survey responses are influenced by these summary data reports (contamination

[figure not shown]
effects), they will be provided to control arm SMEs after the employee survey has been conducted at each time point (baseline, 6, 12 and 18 months). This approach has been successfully applied in the NIHR-funded IGLOO study to secure engagement from control organisations. Additionally, once all study data has been gathered, control SMEs will also be invited to nominate an employee for work and health training to transfer new knowledge and skills into the control SMEs.

Together, these services would otherwise cost at least £5,000 per SME, representing an attractive financial offer to control SMEs.

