9.1.2 METHOD and DATA

Quantitative data to be collected (Participant-level data)

Participant questionnaires

In addition to the collection of screening and consent data, immediately following consent, all participants (both in the intervention and control SMEs) will be invited to complete a baseline study questionnaire (database form 3) using the same REDCap link enquiring into work engagement (primary outcome) and secondary outcomes (as per WP1 above).

Our data collection methodology and design will consider survey fatigue and time constraints on SME employees, aiming for completion within 15 minutes. Data collection tools will capture information on work engagement (primary study outcome) and various secondary outcomes (encompassing health and occupational measures, and resource use-/cost-related measures) along with other co-variates (e.g. demographic characteristics and organisational factors). These could include:

Demographics

- Age
- Sex
- Job role

Health outcomes

- Primary outcome: Work Engagement (UWES)
- Secondary outcomes:
 - Health-related quality of life (e.g. EQ-5D-5L)
 - Mental wellbeing (WHO-5)
 - Health behaviours (7-Day Physical Activity Recall Question)
 - Safety behaviours (Work Safety Scale (WSS))

Occupational outcomes

- “Employees’ perspective” (single item job satisfaction)
- “Employers’ perspective” (productivity (WPAI scale)) Resource use measures
- SMEs and LEOs: Financial investment and time investment (of management and paid time of employees) in HWS scheme and specific resources used in the delivery of the intervention
- Employees: Financial investment (purchasing additional materials to support their involvement in the intervention and changes in their lives outside of the workplace, e.g. signing up to the gym) and time investment outside of paid work time.
- Wider economy: DOH (e.g. GP appointments, hospital visit) and DWP (e.g. social security expenditures)

In the middle of the 12-month intervention period (6-months), participants will be invited to complete a short survey, which will ask about the primary outcome (work engagement) and, if they are in the intervention arm, will also ask if they are aware of all available HWS offers, if they have engaged with any of the offers, and their interim thoughts on these offers. At the end of the 12-month intervention period, and at 18 months, all study participants will complete a follow-up questionnaire (database form 4 & form 5) like that at baseline, with

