further questions about engagement with specific components of the HWS for those in the intervention group (supplementary Fig 2).

Implementation of Organisational Engagement Activity Log

Throughout the HWS intervention implementation period, intervention fidelity and participants' engagement related activities will be monitored and documented using an online engagement activity log. The activity log will serve three purposes:

i) To act as a central repository for all SHINE activity within each SME. Recognising that each SME is likely to have different ways of working and communication channels, and each H&W Champion is likely to have multiple demands on their time, the activity log will allow information to be gathered in a consistent way across organisations, and act as a live 'to do' list and activity log for both the H&W Champion and their Advisor to keep track of progress.

ii) It is envisaged that the H&W Champions and the Advisor will use the activity log as a platform for discussion during monthly meetings, optimising the value of the study through the early identification of implementation issues and facilitating identification of practical actions to be taken to overcome challenges.

iii) It will provide an opportunity to monitor the HWS intervention implementation, intervention fidelity and participants' engagement in related activities, and will be analysed in the process evaluation and triangulated with qualitative and quantitative data gathering (WP4).

NOTE: To ensure participant confidentiality, NO personal identifiable information will be recorded in this activity log.

Data handling and recording keeping

SURVEY DATA

During conduct of this study, the research team will not disclose or make use of any information other than for its intended purpose. All survey data will be collected and initially stored using sponsor approved REDCap (electronic software database) and access to the source data within the software portal will be password protected, and only accessible by authorised persons i.e. central study team only. A back-up paper-based survey will be available upon request and on their return to the study team using a business reply envelope, data will be entered by the research team into the REDCap database and paper records will be securely stored by the research team in a locked cupboard in the Occupational Health, Safety and Wellbeing Service at Guy's and St Thomas NHS Foundation Trust) prior to long-term storage.

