Questionnaire responses will be converted into relevant outcome metrics (e.g. work engagement score, health economic utility scores). Employee-level outcome data collected at baseline, 6 months, 12 month and 18 months will be analysed using two-level multilevel regression models, with employee participants nested within SMEs. Analyses will include an interaction term between the intervention group and time period, to assess differences in change in work engagement (and then separately for each of the secondary outcome measures) between baseline, 6-months (work engagement only) and 12 months (i.e. short-term intervention effect), and between baseline and 18 months (long-term intervention effect) between the intervention and the control SMEs.

Further analyses will assess effect modification by organisational (information collected at the recruitment process like workforce size, sector, relative size of customer, and length of business operation) and intervention delivery factors (dependent on the variation in the recruited SMEs), including a multiplicative interaction between intervention group and each of the factor under consideration. If there is evidence of significant effect modification, we will stratify our analyses accordingly to determine the strength and the direction of the effect by levels of the modification factor.

Economic evaluation will take the form of a cost-consequence analysis (whereby disaggregated non-monetised changes in outcomes are presented alongside costs to inform decision making) and a Social Return on Investment (SROI) [24,25], whereby benefits observed after 12 and 18 months are monetised using published sources, and potential longer-term impacts are explored using different assumptions about the sustainability of changes in behaviour and health. Resources used in intervention delivery will be assessed using data collected in WP2 and costed using a micro-costing approach [26]. Resources used by companies and employees will be assessed using questionnaire data (example measures listed above in WP1), and costs incurred will be calculated using relevant unit cost data. Differences in the results will also be presented in terms of the person- and SME-level moderators defined above and the perspective of the analysis, which will include the employer, employee and wider economy perspectives.

Engagement activity log

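### Section 9.3 tests intervention-delivery factors as effect modifiers although some can exist only in intervention SMEs, and re-fits the model in strata of few SMEs when an interaction is significant

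*Protocol*

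**What the plan says.** Section 9.3 of the protocol (Analysis, WP2-4) sets the main model: two levels, employees within SMEs, with a group-by-time interaction. It then adds further analyses of effect modification. The organisational factors are illustrated by "workforce size, sector, relative size of customer, and length of business operation". The same sentence adds "intervention delivery factors (dependent on the variation in the recruited SMEs), including a multiplicative interaction between intervention group" and each factor. One follow-on rule covers both kinds of factor: "If there is evidence of significant effect modification, we will stratify our analyses accordingly".

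Other sections show where delivery data arise. Section 8.1.3 states: "Control arm SMEs will not receive the intervention". Section 7.1.6 recruits champions in intervention SMEs only, and section 9.1.2 has the champion hold the activity log. The 6-month survey, "if they are in the intervention arm, will also ask if they are aware of all available HWS offers"; the 12- and 18-month questionnaires add "further questions about engagement with specific components of the HWS for those in the intervention group".

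The second study objective includes exploring what may alter the intervention effect, and section 9.1.3 lists a set of moderating factors among the WP3 outputs.

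**The concern.** Effect modification asks whether the contrast between randomised arms differs across levels of a factor, so the factor needs a value in both arms. Uptake, number of activities or champion effort has no value in an SME that was offered nothing. It also arises after randomisation, and it reflects the SME: section 8.1.2 tailors the package to each SME's needs and existing services. A more engaged workforce may both take up more and score higher.

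If section 9.3 is followed literally for such a factor, the software will drop a term or drop the control arm. What remains could then enter the list of moderators, and the moderator-specific economic results that section 9.3 also promises, as though randomisation supported it. Separately, the stratification rule sends any significant factor, organisational ones included, into separate fits on few clusters, selected by a significance test.

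**Working it through.** **1. Can the stated interaction be estimated?** Let G = 1 for intervention and 0 for control, and let D be a delivery factor, 0 in all controls. Then G x D = D for every SME, so the design [1, G, D, G x D] has two identical columns.

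- 18 SMEs (9 per arm): rank 3 of 4. 24 SMEs (12 per arm): rank 3 of 4.
- With three follow-up time terms crossed with all four columns: rank 12 of 16.
- With D coded missing in controls, only intervention SMEs remain and G itself is lost.
- With an organisational factor known in both arms: rank 4 of 4, so estimable.

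Strata by level of D fail in the same way. Every level above zero contains intervention SMEs only, so there is no between-arm contrast inside it.

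**2. The protocol's own planning figure.** Inputs from section 8.1.6: means 5.08 and 5.76 (difference 0.68), SDs 1.40 and 0.86, rho 0.1, average 65 employees per SME, 90% power, two-sided 5%.

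- Sum of variances: 1.40² + 0.86² = 2.6996. Design effect: 1 + 64 x 0.1 = 7.4.
- k = (1.960 + 1.282)² x 2.6996 / 0.68² x 7.4 / 65 = 6.98, so 7 SMEs per arm. The stated figure reproduces.

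**3. Power inside a stratum.** The same inputs, with a noncentral t on 2k - 2 degrees of freedom because there are few clusters. For equal clusters, SE = √(2.6996 x 7.4 / (65k)). For sizes spread evenly over 5 to 125, the effective size per SME, m / (1 + (m - 1) x 0.1), averages 8.29 (against 65 / 7.4 = 8.78), so SE = √(2.6996 / (8.29k)).

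| SMEs per arm in stratum | SE, equal / unequal sizes | Power for 0.68, equal / unequal |
|---|---|---|
| 3 | 0.320 / 0.329 | 37% / 35% |
| 4 | 0.277 / 0.285 | 54% / 52% |
| 6 | 0.226 / 0.233 | 77% / 75% |
| 9 (all 18 SMEs) | 0.185 / 0.190 | 93% / 92% |
| 12 (all 24 SMEs) | 0.160 / 0.165 | 98% / 98% |

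Three or four per arm is what a split by LEO would give (section 7.1.5). Six per arm is an even two-way split of 24 SMEs. At 3 per arm the 95% interval has a half-width of about 2.776 x 0.320 = 0.89, wider than the planning difference.

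**4. Power of an organisational interaction.** For a binary factor split evenly, SE = √(4v / (K/2)), with K SMEs per arm and v = (2.6996 / 2) x 7.4 / 65 = 0.1537.

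- K = 9: SE 0.370. Power is 40% if the effect differs by 0.68 between levels; the difference detectable with 80% power is about 1.11.
- K = 12: SE 0.320. Power is 52%; the detectable difference is about 0.94.

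**The case against.** The protocol names no delivery factor. The examples of uptake and champion activity are mine, inferred from the data it collects. A delivery-related factor known in both arms before randomisation, such as the delivering LEO, would give an estimable interaction. This stands, and it limits the point to factors that exist only in the intervention arm. But section 9.3 does not confine its list to factors defined in both arms, and the delivery data it arranges to collect come from intervention SMEs.

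A second reply is that the rank failure does not remove all information. Drop the redundant column and [1, G, D] has full rank, with a coefficient for D. That is correct. A reader might infer that nothing about delivery can be learned; that goes too far. The coefficient is the gradient across the 9 to 12 intervention SMEs. It is estimable but not randomised.

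Third, 3 or 4 SMEs per arm is the unfavourable case. LEO is not among the listed factors, SME sector is collected separately, and a two-level factor leaves larger strata. This also stands, so the sizes above are a range. Nor are the strata small in employees: at 65 per SME, a LEO stratum of 6 to 8 SMEs has about 390 to 520. The shortage is in clusters.

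Finally, requiring a significant interaction before showing subgroup effects is a recognised safeguard, and the text already presents this work as exploratory and additional. Both are fair. Neither makes a separate re-fit better than reading level-specific effects from the interaction model, which uses all SMEs.

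**Conclusion.** The point holds for delivery factors that exist only in intervention SMEs. For these, the stated group-by-factor interaction is not identified, the stratified analysis has no controls at any delivered level, and what can be estimated is a non-randomised association over 9 to 12 SMEs. It should not be reported as effect modification.

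The documents do not support the wider inference that the whole effect-modification analysis fails. Organisational interactions are estimable, with 40-52% power for a between-level difference as large as the full planning effect. Stratified re-fits are imprecise to a degree that depends on the factor: about 35-37% power at 3 per arm, 52-54% at 4 and 75-77% at 6. The primary comparison is untouched.

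The power figures assume the protocol's SDs and rho, the cluster sizes shown, and no gain from baseline adjustment or matching. The rank result needs only that the factor is zero or undefined in every control SME.

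**What to change.** In section 9.3:

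1. Restrict group-by-factor (by time) interactions to pre-randomisation factors defined in both arms, and name them.
2. Replace the significance-triggered stratification with level-specific effects and confidence intervals from the single interaction model, whatever the test result.
3. Analyse delivery factors separately within the intervention arm, report them as non-randomised associations, and keep them out of the list of moderating factors.

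The cost is a wording change and a small within-arm analysis, with no new data. The downside is that no randomised moderation claim can be made for delivery factors, which the design could not have supported in any case.

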5 TRIAL OBJECTIVES AND PURPOSE

Aims and Objectives

The study aims to assess the effectiveness of HWS delivered by LEOs to SMEs in their supply chain on improving work engagement, and to explore SME decision makers' and large organisations' willingness and capacity to engage with and pay for HWS offered this way.

The study objectives are to: 1) establish what HWS can be delivered by LEOs to SMEs in their supply chain; 2) evaluate the effectiveness of HWS delivered by LEOs to SMEs in their supply chain and explore factors that may affect the intervention effect on outcomes when compared to control arm SMEs; 3) conduct an economic evaluation using cost-consequence and social return on investment (SORI) frameworks to compare the intervention benefits and costs; 4) conduct a process evaluation to monitor implementation and perceptions by stakeholders in SMEs and LEOs; 5) assess the willingness and capacity of SMEs to engage and pay for HWS through this model.

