8.1.5 STUDY FLOW DIAGRAM (INTERVENTION and CONTROL ARM)

8.1.6 Participant Selection

Participants recruited into the study will be drawn from the 18-24 SMEs recruited to take part in the study and we will work with the local collaborator at each SME to develop an acceptable method to invite participants to take part. We will monitor recruitment from each participating centre and will relay information back to the local sites, so they are aware of the recruitment uptake.

Sample size calculation and justification

A previous study of a workplace intervention to build and sustain work engagement [27] suggests a mean (SD) work engagement score of 5.08 (1.40) in the control and 5.76 (0.86) in the intervention group. As the proposed intervention is SME-based, sample size calculations must account for clustering effects. With the rho of 0.1 and the above values for expected change in work engagement scores, seven SMEs per intervention arm ensure 90% power at a 5% significance level (2-sided) to detect differences in the primary outcome. To account for participant attrition, we plan to over-sample with nine to twelve SMEs per arm, depending on the availability of interested SMEs, and to maximise the recruited employee sample per SME.

Given the workforce size of SMEs (between 10 and 249 employees), and assuming a uniform response rate across the recruited SMEs no greater than 50%, the anticipated number of participating employees per SME will range from 5 to 125, equivalent to an average of 65 employees per SME. Put together, the anticipated sample size across the minimum of 18 recruited SMEs would be 1170 employees, rising to 1560 employees if we can recruit the full complement of 24 SMEs. This ensures robustness in detecting meaningful changes in work engagement attributable to the proposed intervention.

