- ii) Study engagement activity log (WP2)
- iii) List of study implementation challenges and changes made (WP2)
- iv) Resources used by SMEs and LEOs in intervention delivery (WP2)
- v) Effectiveness analysis results (WP3)
- vi) List of factors that moderate impact of intervention (WP3)
- vii) Economic evaluation including Social Return on Investment (SROI)(WP3)

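### Effect modification is screened with a group-by-factor term that omits time, although the intervention effect is defined as group-by-time, so the screen tests the wrong quantity and can miss true moderators

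*Protocol*

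**What the plan says.** Section 9.3 (Analysis, WP2-4) puts all survey waves, baseline among them, into two-level models with employees nested in SMEs. It defines the effect as follows: "Analyses will include an interaction term between the intervention group and time period, to assess differences in change in work engagement". The short-term effect is the contrast of baseline with 6 and 12 months, and the long-term effect is baseline with 18 months. Secondary outcomes are not collected at 6 months.

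The next paragraph of 9.3 turns to effect modification by organisational factors (workforce size, sector, relative size of customer, length of operation) and by delivery factors. The term it names is "including a multiplicative interaction between intervention group and each of the factor under consideration". If that is significant, the analyses are to be stratified by the factor.

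The test serves objective 2 in section 5, to "explore factors that may affect the intervention effect on outcomes when compared to control arm SMEs". Section 9.1.3 lists the resulting set of moderators as a WP3 output, and 9.3 also presents the economic results by these moderators.

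**The concern.** If the effect is a difference in change over time, then modification of that effect is a difference, between levels of the factor, in the difference in change. That is the group-by-time-by-factor term. A group-by-factor product in a model that keeps baseline as an outcome wave answers another question: does the gap between arms in average score level depend on the factor? One of the averaged waves precedes the intervention, so it adds no signal. The stable part of the between-SME differences, which a change score removes, stays in the error.

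The paragraph is also inconsistent with itself. The gate tests score levels, while the stratified analyses that it opens would estimate group-by-time effects. A true moderator that fails the gate is never examined further, although finding moderators is a stated objective. The point concerns the organisational factors, which exist in both arms.

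**Working it through.** **Inputs from section 8.1.6.** Means and SDs are "5.08 (1.40) in the control and 5.76 (0.86) in the intervention group"; rho is 0.1; the cluster size is "equivalent to an average of 65 employees per SME"; there are 18 to 24 SMEs; the test is two-sided at 5%. The difference is 0.68 and the pooled variance is (1.40² + 0.86²)/2 = 1.350 (SD 1.162).

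**The plan's own figure.** n per arm = 2 × 1.350 × (1.960 + 1.282)² / 0.68² = 61.3. Design effect = 1 + 64 × 0.1 = 7.4. Then 61.3 × 7.4 / 65 = 6.98, so seven SMEs per arm for 90% power. The stated figure reproduces. It covers the main effect; no figure is given for effect modification.

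**Dilution (needs no outside figure).** Let a modification θ be present at every follow-up and absent at baseline. Averaged over waves:
- work engagement, four waves: (0 + θ + θ + θ)/4 = 3θ/4, so 0.68 becomes 0.51;
- secondary outcomes, three waves: (0 + θ + θ)/3 = 2θ/3.

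**Power (assumptions not in the protocol).** θ = 0.68 (the whole planned effect in one level of the factor, none in the other); a two-level factor split evenly in both arms; the same 65 employees per SME at each wave; within-employee correlation r of 0.5–0.7; a share c of between-SME variance that is stable over time.

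Between-SME variance B = 0.1 × 1.350 = 0.135. Within-SME variance of an SME mean W = 0.9 × 1.350 / 65 = 0.0187. With K SMEs in four equal cells, the contrast has variance 16V/K and is tested on K − 4 df, where V is:
- two-way term (average level): B[c + (1−c)/4] + W[r + (1−r)/4], expected value 0.51;
- three-way term, 12 months minus baseline: 2(1−c)B + 2(1−r)W, expected value 0.68;
- three-way term, mean of three follow-ups minus baseline: (4/3)[(1−c)B + (1−r)W], expected value 0.68.

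Example, K = 24, c = 0.8, r = 0.6. Two-way: V = 0.1278, SE = 0.292, power 38%. Three-way at 12 months: V = 0.0689, SE = 0.214, power 85% (84–87% for r from 0.5 to 0.7).

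Power (%) at r = 0.6:

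| Stable share c | 24 SMEs: two-way | 12-month three-way | averaged three-way | 18 SMEs: two-way | 12-month three-way | averaged three-way |
|---|---|---|---|---|---|---|
| 1.0 | 34.0 | >99 | >99 | 25.9 | >99 | >99 |
| 0.9 | 36.0 | 97.2 | >99 | 27.4 | 90.5 | 97.9 |
| 0.8 | 38.4 | 85.5 | 95.8 | 29.2 | 72.4 | 87.8 |
| 0.5 | 47.8 | 53.5 | 70.8 | 36.5 | 41.1 | 56.5 |
| 0.2 | 63.1 | 37.8 | 52.4 | 49.4 | 28.8 | 40.2 |
| 0 | 78.4 | 31.8 | 44.4 | 64.3 | 24.2 | 33.8 |

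Simulation of SME means agreed with these values. A mixed model fitted literally as described (24 SMEs, 30 employees each, 150 runs) gave a mean group-by-factor estimate of 0.53 for a true 0.68, and power of about 43%.

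**False positives.** With no modification, all three tests reject about 5% of the time. Only when the baseline group-by-factor contrast happens to lie more than 1 SD from zero (0.32 points with 24 SMEs, 0.37 with 18) does the two-way term reject about 15% of the time, against 6–7% for the three-way term (c = 0.8). Lower rejection in the remaining trials offsets this.

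**The case against.** The strongest reply is that 9.3 is written in summary. The only effect defined is group-by-time, so a sentence about modifying the effect may be shorthand for adding the factor to that term, with the model formula left to an analysis plan that is not at hand. This may be what the authors mean. But the protocol names the group-by-time product explicitly and, one paragraph later, names a different product. An analyst following the text would fit the two-way term. That is a stated term that does not match the stated effect, which differs from detail left open.

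Other parts of the reply stand and limit the point:
- A reader might infer that the moderator list will mainly reflect how SMEs differed at the start. The documents do not support this: SMEs are randomised within pairs (section 7.1.5), and the overall false-positive rate stays near 5%.
- A reader might infer that moderators will be understated when reported. Effects by level come from the stratified group-by-time analyses, where baseline is removed and the 3/4 factor does not apply. Those analyses would also tend to expose a pure baseline imbalance.
- A reader might infer that true moderators are mostly missed. That depends on how stable SME-level scores are over time, which the protocol does not give, and on a large assumed modification. By a stable share of 20% the two-way term is the more powerful.
- The calculation ignores the pairing by LEO and workforce size, and workforce size is itself one of the factors.
- The aim is exploratory, and the primary comparison and its sample size do not depend on this test.

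**Conclusion.** The point holds as a mismatch between the defined effect and the term named to test its modification. The wrong quantity and the dilution to 3/4 (2/3 for secondary outcomes) in the screening coefficient follow from the text, given a modification present at all follow-ups.

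The size of the power loss is conditional. It is large where SME effects are mostly stable, and a two-level model with a single SME intercept implies full stability. It is slight against the 12-month term at a stable share of one half (about 4 to 7 points with 24 SMEs), and it turns into a gain at low stability. The harm is a gate that can miss true moderators. It does not amount to an inflated rate of false moderators or to diluted final estimates.

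**What to change.** In section 9.3, state that effect modification by each organisational factor is tested by the interaction of intervention group, time period and factor, with all lower-order terms, at the 12- and 18-month contrasts and with 95% confidence intervals. An acceptable alternative is group-by-factor on follow-up scores adjusted for baseline.

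This needs no new data and leaves the primary analysis alone. The cost is a few more model terms per factor, and a smaller gain, or a loss, of power if SME-level scores prove unstable over time.
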